2.0 BACKGROUND

2.1 Introduction and rationale for development of chemotherapy backbone for de novo AML

Overall survival (OS) rates in pediatric acute myeloid leukemia (AML) approach 65-70% at three years with the current risk adapted chemotherapy and hematopoietic stem cell transplantation (HSCT) approach¹. The recently concluded Children's Oncology Group (COG) trial in pediatric de-novo AML AAML1031 (2011 – 2017) and its precursor trial AAML0531 (2006 – 2010) used a chemotherapy backbone adapted from the Medical Research Council (MRC) AML trials in order to improve overall outcomes²⁻⁴. This backbone comprised of an induction course of chemotherapy with cytarabine, daunorubicin and etoposide. Patients were risk stratified into low, intermediate and high risk groups on AAML0531 based on their cytogenetic and molecular features and their response at the end of this first cycle of induction chemotherapy¹. Patients on AAML0531 received 5 cycles of chemotherapy if they did not meet criteria for consideration of HSCT in first remission (Table 1). In addition, patients were randomized to receiving gemtuzumab ozogamicin (GO) at study entry and received this drug along with chemotherapy in Induction 1 and Intensification 2. Based on results from the MRC12 trial and preliminary analysis of AAML0531, the fifth course of chemotherapy was deleted from the chemotherapy backbone for AAML1031³. The risk stratification evolved over the years with the improvement in multi-dimensional flow cytometry (MDFC) and AAML1031 stratified patients into low and high risk categories using response defined by MDFC (measurement of minimal residual disease –MRD) in addition to cytogenetic and molecular features⁵.

2.1.1 Rationale for chemotherapy approach in children with low risk AML

Based on the recent COG AAML1031 chemotherapy backbone, patients with low-risk AML received Induction II that is similar to Induction I and two more cycles of consolidation therapy which included two high-dose cytarabine ($> 1\text{gm}/\text{m}^2$ per dose) courses in Intensification 1 and Intensification II. Patients with high-risk AML received an intensified second course (Induction II) of chemotherapy comprising of mitoxantrone and high dose cytarabine followed by two more high dose cytarabine containing courses (Intensification I and II) if allogeneic hematopoietic stem cell transplantation was not an option. Thus, these high-risk patients received a total of three courses with high-dose cytarabine as opposed to the low-risk patients who only received two. In addition, in the COG approach, low-risk AML patients received higher doses of anthracycline ($492\text{ mg}/\text{m}^2$) and etoposide ($1.75\text{ g}/\text{m}^2$) as compared to high-risk patients who did not receive a stem cell transplant². Exposure to high doses of anthracycline and etoposide results high risk of cardiotoxicity and secondary malignancies with the cardiotoxicity risk being highest in patients with acute myeloid leukemia^{6,7}. Mertens et al demonstrated that in the Childhood Cancer Survivor Study, cardiac causes and secondary malignancies accounted for excess mortality rates in the childhood cancer survivors as compared to the general population⁸. Cumulative anthracycline dosage $>300\text{ mg}/\text{m}^2$ was associated with increased incidence of anthracycline-induced clinical heart failure⁹ thereby raising concerns that exposures as high as $492\text{ mg}/\text{m}^2$ in this low-risk cohort on AAML1031 could place them at very high risk of heart failure.

Patients with low-risk AML have favorable outcomes (3-year EFS and OS - 70% and 85% respectively) as compared to patients with high-risk AML (3-year EFS and OS – 30% and 48% respectively)¹. Regardless of risk, disease relapse still remains the major cause of mortality¹. Anthracyclines comprise an important component of relapsed AML therapy and higher doses of anthracyclines received in upfront AML therapy preclude their use at the time of relapse¹⁰. Given the concerns for long term toxicity without clear evidence of benefit to additional anthracyclines and etoposide in low-risk AML patients, we chose to adopt an institutional approach (Aflac-AML regimen) whereby newly diagnosed low-risk AML patients were treated with four cycles of chemotherapy that was identical to the high-risk group per AAML1031 which received chemotherapy alone. The aim of our regimen was to limit anthracycline exposure to 342 mg/m² and etoposide exposure to 1.25 g/m² in low-risk AML patients while maintaining the same favorable outcomes. A comparison of the two regimens is outlined in the table (Table 1) below.

Table 1: Therapy regimen for Aflac-AML, AAML0531 and AAML1031 low-risk patients

[figure not shown]
Aflac-AML		COG AAML0531		COG AAML1031	
Induction 1					
Cytarabine	100 mg/m ² /dose every 12 hours IV Days 1-10	Cytarabine	100 mg/m ² /dose every 12 hours IV Days 1-10	Cytarabine	100 mg/m ² /dose every 12 hours IV Days 1-10
Daunorubicin	50 mg/m ² /dose IV Days 1, 3, 5	Daunorubicin	50 mg/m ² /dose IV Days 1, 3, 5	Daunorubicin	50 mg/m ² /dose IV Days 1, 3, 5
Etoposide	100 mg/m ² /dose IV Days 1-5	Etoposide	100 mg/m ² /dose IV Days 1-5	Etoposide	100 mg/m ² /dose IV Days 1-5
Induction 2					
Cytarabine	1,000 mg/m ² /dose every 12 hours IV Days 1-4	Cytarabine	100 mg/m ² /dose every 12 hours IV Days 1-8	Cytarabine	100 mg/m ² /dose every 12 hours IV Days 1-8
Mitoxantrone	12 mg/m ² /dose IV Days 3-6	Etoposide	100 mg/m ² /dose IV Days 1-5	Etoposide	100 mg/m ² /dose IV Days 1-5
----	----	Daunorubicin	50 mg/m ² /dose IV Days 1, 3, 5	Daunorubicin	50 mg/m ² /dose IV Days 1, 3, 5
Intensification 1					
Cytarabine	1,000 mg/m ² /dose every 12 hours IV Days 1-5	Cytarabine	1,000 mg/m ² /dose every 12 hours IV Days 1-5	Cytarabine	1,000 mg/m ² /dose every 12 hours IV Days 1-5
Etoposide	150 mg/m ² /dose IV Days 1-5	Etoposide	150 mg/m ² /dose IV Days 1-5	Etoposide	150 mg/m ² /dose IV Days 1-5
Intensification 2					
Cytarabine	3,000 mg/m ² /dose every 12 hours IV Days 1, 2, 8, 9	Cytarabine	1,000 mg/m ² /dose every 12 hours IV Days 1-4	Cytarabine	1,000 mg/m ² /dose every 12 hours IV Days 1-4
Erwinia L-Aspargnase	25,000 International Units/m ² /dose IM Days 2, 9	Mitoxantrone	12 mg/m ² /dose IV Days 3-6	Mitoxantrone	12 mg/m ² /dose IV Days 3-6
Intensification 3					
----	----	Cytarabine	3,000 mg/m ² /dose every 12 hours IV Days 1, 2, 8, 9	----	----
----	----	E. Coli L-Aspargnase	6,000 mg/m ² /dose IM Days 2, 9	----	----

Abbreviations: COG, Children's Oncology Group; IM, intramuscular; IV, intravenous

We performed a retrospective review of our institutional cohort of patients with de novo low-risk AML between 0-21 years of age at diagnosis and were treated at the Aflac Cancer and Blood Disorders Center at Children's Healthcare of Atlanta (CHOA) between January 1, 2011 and

December 31, 2016 (manuscript in progress). LR-AML was defined as the presence of NPM1, CEBPA, t(8;21)(q22;q22), inv(16)(p13.1q22), or less than 0.1% blasts (minimal residual disease – MRD negative) at end of Induction I, with the absence of unfavorable cytogenetic or molecular findings. A total of 27 patients with LR-AML treated per Aflac-AML were eligible for analysis with a mean follow up period from time of diagnoses of 3.3 years (SD 2.0). For the study population three-year EFS and OS from end of Induction 1 were $70.0\% \pm 0.1\%$ and $85.5\% \pm 0.08\%$ (Figure 1A and B).

Figure 1 A and B: EFS and OS for low-risk patients treated on Aflac-AML regimen

Given that our rates of treatment associated infection are comparable to published standards along with similar favorable outcomes, we will plan to use our described four cycle cytarabine-intensive regimen piloted in 27 patients as the chemotherapy backbone for this trial. All patients regardless of risk status will receive mitoxantrone-cytarabine as their second course of therapy (Induction II). This will be followed by Intensification I (cytarabine-etoposide) and Intensification II (Capizzi-AraC) for low-risk patients. Patients with high-risk disease will receive an allogeneic HSCT typically after two or three courses of chemotherapy. The third course could be either cytarabine-etoposide or Capizzi-AraC at the treating physician's discretion. High-risk patients unable to receive a HSCT will receive treatment per the Aflac-AML regimen with four cycles of chemotherapy similar to low-risk AML patients.

2.2 Rationale for incorporation of Gemtuzumab Ozogamicin (GO)

Gemtuzumab Ozogamicin (GO, Mylotarg™) is an antibody-drug conjugate (ADC) chemotherapy agent that is composed of a recombinant humanized IgG4, kappa antibody to CD33 conjugated with a cytotoxic antitumor antibiotic, calicheamicin¹¹. It binds to CD33 after which the complex is endocytosed and undergoes dissociation in the lysosome. The detached calicheamicin then binds to the minor groove of cellular DNA causing damage and apoptosis¹². It received accelerated approval in May 2000 by the US FDA for treatment of older adults with CD33 positive AML in first relapse not considered candidates for cytotoxic therapy¹³. CD33 expression is absent on normal

hematopoietic stem cells and is limited to leukemic blasts, thus making it an attractive therapeutic target¹⁴.

Though GO was initially approved for use in patients experiencing first relapse of AML who were unable to tolerate any other chemotherapy, it was subsequently given both as monotherapy and in combination with other chemotherapy agents for patients with *de novo* AML¹⁵⁻¹⁸. Myelosuppression, infections, hyperbilirubinemia and elevated liver enzymes were the major side effects reported¹⁹. Hepatic veno-occlusive disease (VOD) was reported in patients who received the drug even in the absence of stem cell transplantation²⁰. However, the Southwest Oncology Group (SWOG) study S0106 which prospectively compared the benefit of adding GO to a standard induction regimen of cytarabine and daunorubicin failed to show any survival benefit and reported a 5% induction mortality in the GO group as compared to the non-GO group (1% mortality)²¹. Results of this study led to the withdrawal of the drug from the market in June 2010. Four subsequent studies demonstrated contrasting results showing efficacy of GO in patients with newly diagnosed AML, supporting the consideration for re-approval of GO in AML²². In the Children's Oncology Group (COG) randomized phase III trial for pediatric patients with *de novo* AML (AAML0531), GO significantly improved the 3-year event free survival (EFS) by reducing the relapse risk (RR), but had no impact on overall survival¹. Specifically in patients with FLT3-ITD positive disease, exposure to GO prior to HSCT reduced the risk of relapse significantly compared to those that had not received GO (15% versus 55%, p=0.007)²³. Following the overwhelming support for the use of GO in AML, the US FDA granted approval for the drug in de-novo and relapsed or refractory disease in September 2017.

Pollard et al divided all patients on AAML0531 based on their CD33 expression into quartiles. Patients with high CD33 expression (Q2-4) had significantly improved EFS and relapse risk²⁴. Single nucleotide polymorphisms (SNPs) in CD33 (specifically resulting in increased number of T alleles) showed a positive correlation with poorer response to GO-containing regimens²⁵. On the COG AML pilot study AAML 03P1, coding SNPs in CD33 (rs35112940 and rs12459419) were associated with better risk disease and improved outcomes compared to other genotypes²⁶. Further characterization and testing in a larger cohort of patients on AAML0531 (n=816) showed that patients with CC genotype (rs12459419) have a significant response to GO as compared to CT or TT genotypes²⁷. When genotyping data was correlated with expression, it was found that the presence of T allele (CT/TT) genotype strongly correlates with low expression of CD33. There are 256/816 patients (31%) who had either CT or TT genotype and were in the high expression (Q2-4) group on AAML0531. In this group, addition of GO did not improve relapse risk. Conversely, there were 61/816 individuals (7%) who were CC genotype that showed low quartile (Q1) CD33 expression. The RR even in this small group was still improved significantly with GO through the p-value was just shy of statistical significance (p=0.055)²⁷. While determination of CD33 expression is universally possible with routine multi-dimensional flow cytometry, division of the data acquired into quartiles that are validated and can be compared between institutions is challenging. Given that the CD33 genotyping shows strong correlation with relapse risk regardless of CD33 expression, we will be obtaining CD33 genotyping on all patients at the time of diagnosis. We expect the turn-around time for this testing to be approximately 4-5 days, allowing for a single 3 mg/m² dose of GO to be administered between days 6-10 during Induction I for patients with CC genotype.

2.3 Rationale for use of Dexrazoxane with anthracyclines

Cumulative incidence of heart failure and other cardiac events in patients with acute leukemias ranges from 4-10% at 10-20 years from diagnosis^{28,29}. While late cardiotoxicity has been

described well following anthracycline exposure above 250-300 mg/m² doxorubicin equivalents, early cardiotoxicity is a growing concern³⁰. Evaluation of cardiotoxicity (defined as grade 2 or higher left ventricular dysfunction per CTCAE version 5.0) on COG AAML0531 showed an incidence of 12% over a five-year follow-up period with most of the events occurring while on protocol therapy. Black, older patients (>1 year age) and concurrent infection were risk factors associated with worse cardiac outcomes³⁰.

Dexrazoxane is a bis-dioxopiperazine compound that was introduced in the early 1990's and has been shown to reduce cardiotoxicity related to anthracyclines initially in animal models and later in clinical studies^{31,32}. While the exact mechanism is poorly understood, it is believed that anthracyclines form complexes with heavy metals specifically iron and generate free radicals that cause cardiac damage³³. Dexrazoxane binds to iron and prevents the generation of free radicals thereby reducing cardiotoxicity. Dexrazoxane has been used successfully in combination with various chemotherapy regimens with acceptable toxicity and enhanced cardio-protection^{34,35}. While there was concern regarding development of secondary malignancies with exposure to dexrazoxane, recent literature has not supported this side-effect³⁶. In this study, all patients will receive dexrazoxane in anthracycline-containing treatment courses. We will closely monitor for infection, cardiac, hepatic and hematologic toxicities as well as development of secondary malignancies. In addition, we will obtain more precise measurements of cardiac function using echocardiogram at the end of each course (Section 8.0) as noted in Table 4.

Table 4: Variables of cardiac function to be determined using echocardiography

Left ventricle (LV) remodeling	LV thickness to dimension ratio
LV myocardial deformation	Strain and Strain rate imaging
LV systolic function	LV Ejection Fraction using biplane Simpson method LV Shortening fraction using 2D and M-mode Mitral and septal S'
LV diastolic function	Early filling peak velocity (E wave) Atrial systole filling peak velocity (A wave) Mitral E/A ratio Isovolumic relaxation time (IVRT) Mitral annular tissue doppler (E' and A') Isovolumic contraction time (IVCT) Aortic ejection time (ET)
LV global function	Spectral Doppler-derived myocardial performance index Tissue Doppler Imaging-derived myocardial performance index

2.4 Use of FLT3-ITD inhibitors in AML

Presence of activating mutations in the FLT3 gene occurs in approximately 15% of pediatric patients with de-novo AML³⁷. Patients with FLT-ITD mutations with a high allelic ratio (HAR>0.4) have an extremely poor progression-free survival of 16% compared to those with lower allelic ratios³⁸ and are therefore categorized in the high risk group post induction. Further analysis of FLT3-ITD mutations has suggested an AR>0.1 to be associated with a poor outcome as well (COG, internal communication). Several FLT3-ITD inhibitors are currently in clinical trials and COG AAML1031 tested the inclusion of one such inhibitor, sorafenib, with the regular chemotherapy backbone in FLT3-ITD positive AML in a non-randomized fashion. The results of this combination are currently under review; however the combination is believed to be safe

(COG, internal communication). In this study, we will use sorafenib as the FLT3 inhibitor of choice in patients with FLT3-ITD HAR (>0.1) AML.

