3.4 Aflac Office Monitoring Schedule

The trial will be monitored internally according to the following schedule:

- Study monitoring will occur every 6 months until all subjects have completed intervention;

- Once all subjects have completed intervention, a final monitoring visit will occur within 90 days after the last study related procedures and follow-up are completed for all patients enrolled;
- Additional monitoring may be performed in the event of serious adverse event(s), if deemed necessary by the monitoring committee or if requested by the Principal Investigator.

4.0 **RISK STRATIFICATION**

After completion of first course of chemotherapy (Induction I), patients will be classified into low or high-risk groups.

Low risk

t(8;21)(q21.3;q22) – CBF (*RUNX1-RUNX1T1*)
 inv(16)/t(16;16)(p13.1q22.1) – CBF (*CBFB-MYH11*)
NPM1 positive without associated *FLT3* mutation
Biallelic CEBPA positive
 No High-Risk Prognostic Markers/MRD negative (<0.05%) at end of 1st induction
CBF, CEBPa, NPM positive **and** MRD positive at the end of 1st Induction

High risk

inv(3)(q21q26.3) *MECOM-RPN1* fusion
 t(3;21)(26.2;q22)
 t(3;5)(q25;q34)
 t(6;9)(p23;q34.1)(*DEK-NUP214*)
 t(8;16)(p11.2;p13.3) *KAT6A*(8p11.21) Fusion (for patients who are 90 days or older)
 t(16;21)(p11;q22) *FUS-ERG*
 Inv(16) (p13.3q24.3) *CBFA2T3-GLIS2*
 Monosomy 7
 Monosomy 5/5q-[*EGR1*(5q31) deleted]
KMT2A(*MLL*) (11q23.3)

- t(4;11)(q21;q23)
- t(6;11)(q27;q23)
- t(10;11)(p11.2;q23)
- t(10;11)(p12;q23)
- t(11;19)(q23;p13.3)

 11p15 rearrangement - *NUP98* (11p15.5)
 12p 13.2 rearrangement - *ETV6* – any partner gene
 Deletion 12p to include 12p13.2
FLT3 High Allelic Ratio mutations (AR >0.1)
 10p12.3 rearrangement - *Non-KMT2A MLL T10 Fusions*
 RAM phenotype (high CD56, dim-to-negative expression CD45 & CD38, no HLA-DR)
 MRD positive (>0.05%) at end of 1st induction, excluding those with *CBF, CEBPa, NPM*

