5.2 Induction 1 for FLT3-ITD patients – ADE (10+3+5) with GO with Sorafenib

The following therapy guidelines are for patients during Induction I with FLT3-ITD mutation. Patients on Induction I will receive gemtuzumab in addition to ADE therapy based on GO genotyping. Induction I lasts a total of 28 days.

Intrathecal Cytarabine: IT

Given at time of diagnostic lumbar puncture or Day 1.

Age-based dosing:

Age (yrs)	Dose
0-0.99	20 mg
1-1.99	30 mg
2-2.99	50 mg
≥ 3	70 mg

For CNS positive patients: add twice weekly IT AraC doses until CNS is clear, plus two additional treatments. A minimum of four intrathecal treatments are to be administered during the period of three weeks following diagnosis.

Cytarabine: Slow IV Push (e.g., over 1-2 minutes)

100 mg/m²/dose (3.3 mg/kg/dose if BSA < 0.6 m²) every 12 hours (total of 20 doses) on Days 1-10.

Daunorubicin (DAUN): IV over 15 minutes

50 mg/m²/dose (1.67 mg/kg/dose if BSA < 0.6 m²) every other day (total of 3 doses) on Days 1, 3, 5.

See Section 6 if direct bilirubin is > 2.

Etoposide (ETOP): IV over 60 – 120 minutes

100 mg/m²/dose (3.3 mg/kg/dose if BSA < 0.6 m²) daily (total of 5 doses) on Days 1-5.

See Section 6 if direct bilirubin is > 2.

Gemtuzumab Ozogamicin (GO): IV over 2 hours

3 mg/m²/dose (0.1 mg/kg/dose if BSA < 0.6 m²) once (total of 1 dose) on Day 6 through 10.

GO to be given once when GO genotyping demonstrates CC genotype. It can be given on any day between days 6-10 of Induction 1.

Pre-medicate with an antihistamine such as diphenhydramine, 1 mg/kg IV (max 50 mg), acetaminophen 10-15 mg/kg PO (max 650 mg) and methylprednisolone (1mg/kg) PO/IV. Repeat every 4 hours as needed to prevent post infusion complications.

Sorafenib (SORAF): PO

Days: 11 through 28.

Dose: 200 mg/m²/dose daily, rounded to accommodate tablet size. The maximum dose will be 400 mg. Dose will be administered per dosing nomogram in Appendix I.

Note: Sorafenib tablets should be taken at least 1 hour before or 2 hours after food. Tablets should be taken with clear liquids (approximately 2 to 4 ounces for children < 12 years and 4 to 8 ounces for \geq 12 years). If taken with food, sorafenib should be taken with a moderate to low fat meal. Tablets should not be crushed and should be swallowed whole. However, sorafenib tablets can be dispersed in water to facilitate the administration to subjects that cannot swallow tablets

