Note: Administer through the tubing of a rapidly infusing solution of D5W or 0.9% NaCl. Avoid extravasation; the use of a central line is suggested. On the Days 3 and 4, mitoXANTRONE should be given 8 hours after the 5th and 7th high dose cytarabine infusions are complete.

Patients with high risk status may proceed to best allogenic donor SCT or alternative donor SCT following Induction II. Depending on timing, these patients may receive a third course of chemotherapy (Intensification I) prior to HSCT. This course could be either AE or HD ARAC/LASP.

Patients with low risk status who had low risk markers and were MRD positive at the end of Induction I and continue to be MRD positive after Induction II will come off protocol.

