5.4 Induction II for FLT3-ITD patients – MA with Sorafenib

The following therapy guidelines are for patients during Induction II with FLT3-ITD AML. Induction II lasts 28 days or longer.

Progression to Induction II should await disease response determination (MRD and extramedullary disease) in order to correctly assign risk stratum. Patients with high or low risk cytogenetic/molecular features may proceed on to Induction II therapy before disease response results are available. By the beginning of Induction II, patients should have been classified as Low or High risk. **If a patient is classified as High risk at the end of Induction I and no family HLA match is found, initiation of an unrelated donor search should occur.**

Intrathecal Cytarabine (IT ARAC): IT

IT ARAC may be administered on Day 1 of Induction II or with the bone marrow evaluation at the end of Induction I.

Age-based dosing:

Age (yrs)	Dose
0 - 0.99	20 mg
1 - 1.99	30 mg
2 - 2.99	50 mg
≥ 3	70 mg

For newly detected CNS positive patients who were CNS negative at diagnosis: IT cytarabine is to be administered twice weekly until the CSF is clear. A minimum of 4 intrathecal treatments must be given and a maximum of 6 intrathecal treatments may be given. Patients whose CSF is clear at the second spinal tap will receive 3 intrathecal treatments once the CSF is clear and all other patients will receive 2 intrathecal treatments once the CSF is clear. Patients with refractory CNS leukemia following 6 doses of therapy will be taken off protocol therapy.

High Dose Cytarabine (HD ARAC): IV over 1 - 3 hours

Days: 1 through 4.

Dose: 1000 mg/m²/dose, every 12 hours (i.e., 2000 mg/m²/day, divided BID) or 33 mg/kg/dose, every 12 hours (i.e., 66 mg/kg/day, divided BID) if BSA < 0.6 m².

Suggested premedications and supportive care: Patients in whom serum creatinine is > 2 mg/dL or > 2 x normal for age, must have a CrCl performed (Day 1) and doses of cytarabine adjusted as outlined.

MitoXANTRONE (MITOX): IV over 15 - 30 minutes

Days: 3 through 6.

Dose: 12 mg/m²/dose or 0.4 mg/kg/dose if BSA < 0.6 m².

Note: Administer through the tubing of a rapidly infusing solution of D5W or 0.9% NaCl. Avoid extravasation; the use of a central line is suggested. On the Days 3 and 4, mitoXANTRONE should be given 8 hours after the 5th and 7th high dose cytarabine infusions are complete.

Sorafenib (SORAF): PO

Days: 7 through 34.

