Dose: 200 mg/m²/dose daily, rounded to accommodate tablet size. The maximum dose will be 400 mg.

Dose to be administered per dosing nomogram in Appendix I.

Note: Sorafenib tablets should be taken at least 1 hour before or 2 hours after food. Tablets should be taken with clear liquids (approximately 2 to 4 ounces for children < 12 years and 4 to 8 ounces for \geq 12 years). If taken with food, sorafenib should be taken with a moderate to low fat meal. Tablets should not be crushed and should be swallowed whole. However, sorafenib tablets can be dispersed in water to facilitate the administration to subjects that cannot swallow tablets.

Patients with FLT3-ITD AML may proceed to best allogenic donor SCT or alternative donor SCT following Induction II. Depending on timing, these patients may receive a third course of chemotherapy (Intensification I) prior to HSCT. This course could be either AE or HD ARAC/LASP with sorafenib.

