5.6 Intensification I for FLT3-ITD patients – AE with sorafenib

The following Intensification I therapy guidelines are for patients with FLT3-ITD AML who do not have an appropriate donor for SCT. Intensification I will last for 28 days or longer. It is suggested, but not required, that patients have an ANC > 1,000/µL and a platelet count > 75,000/µL before proceeding with Intensification I therapy.

Intrathecal Cytarabine (IT ARAC): IT

IT ARAC may be administered on Day 1 of Intensification I or with the bone marrow evaluation at the end of Induction II.

Age-based dosing:

Age (yrs)	Dose
0 - 0.99	20 mg
1 - 1.99	30 mg
2 - 2.99	50 mg
≥ 3	70 mg

High Dose Cytarabine (HD ARAC): IV over 1 - 3 hours

Days: 1 through 5.

Dose: 1000 mg/m²/dose, every 12 hours, (i.e., 2000 mg/m²/day, divided BID), or 33 mg/kg/dose, every 12 hours (i.e., 66 mg/kg/day, divided BID) if BSA < 0.6 m².

Suggested premedications and supportive care: Administer steroid eye drops (0.1% dexamethasone or 1% prednisolone ophthalmic solution), 2 drops to each eye every 6 hours, beginning immediately before the first dose and continuing for 24 hours after the last dose. If patient does not tolerate steroid eye drops, may administer artificial tears on an every 2-4 hour schedule. Patients in whom serum creatinine is > 2 mg/dL or > 2 x normal for age, must have a CrCl performed (Day 1) and doses of cytarabine adjusted as outlined.

Etoposide (ETOP): IV over 60 - 120 minutes

Days: 1 through 5.

Dose: 150 mg/m²/dose, or

5 mg/kg/dose if BSA < 0.6 m².

Note: Slow rate of administration if hypotension occurs. The use of an in-line filter during the infusion is suggested. Each dose of etoposide should immediately follow the 1st, 3rd, 5th, 7th and 9th doses of cytarabine.

Sorafenib (SORAF): PO

Days: 6 through 33

Dose: 200 mg/m²/dose daily, rounded to accommodate tablet size. The maximum dose will be 400 mg.

Dose to be administered per dosing nomogram in Appendix I.

Note: Sorafenib tablets should be taken at least 1 hour before or 2 hours after food. Tablets should be taken with clear liquids (approximately 2 to 4 ounces for children < 12 years and 4 to 8 ounces for ≥ 12 years). If taken with food, sorafenib should be taken with a moderate to low fat meal. Tablets should not be crushed and should be swallowed whole. However, sorafenib tablets can be dispersed in water to facilitate the administration to subjects that cannot swallow tablets.

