5.8 Intensification II for FLT3-ITD patients – HD ARAC/LASP with sorafenib

The following Intensification II therapy guidelines are for patients with FLT3-ITD AML who do not have an appropriate donor for SCT. Intensification II lasts 28 days or longer.

It is suggested, but not required, that patients have an ANC > 1,000/µL and a platelet count > 75,000/µL before proceeding with therapy.

High Dose Cytarabine (HD ARAC): IV over 3 hours

Days: 1, 2 and 8, 9

Dose: 3,000 mg/m²/dose, every 12 hours (i.e., 6,000 mg/m²/day, divided BID), or

100 mg/kg/dose, every 12 hours (i.e., 200 mg/kg/day, divided BID) if BSA < 0.6 m².

Suggested premedications and supportive care: Administer steroid eye drops (0.1% dexamethasone or 1% prednisolone ophthalmic solution), 2 drops to each eye every 6 hours, beginning immediately before the first dose and continuing for 24 hours after the last dose. If patient does not tolerate steroid eye drops, may administer artificial tears on an every 2-4 hour schedule. Patients in whom serum creatinine is > 2 mg/dL or > 2 x normal for age, must have a CrCl performed (Days 1 and 8) and doses of cytarabine adjusted as outlined.

Erwinia L-asparaginase (Erwinaze): IM (may be given IV over 1 hour)

Days: 2, 9 (one dose per day, 2 doses total for the entire course)

Dose: 25,000 IU/m² (830 IU/kg/dose if BSA < 0.6 m²)

Note: Erwinia asparaginase should be given 6 hours after the start of cytarabine doses 4 and 8. If Erwinia asparaginase is not available, pegaspargase should not be given. Rather, asparaginase should be omitted.

Sorafenib (SORAF): PO

Days: 11 through 28.

Dose: 200 mg/m²/dose daily, rounded to accommodate tablet size. The maximum dose will be 400 mg. Dose will be administered per dosing nomogram in Appendix I.

Note: Sorafenib tablets should be taken at least 1 hour before or 2 hours after food. Tablets should be taken with clear liquids (approximately 2 to 4 ounces for children < 12 years and 4 to 8 ounces for ≥ 12 years). If taken with food, sorafenib should be taken with a moderate to low fat meal. Tablets should not be crushed and should be swallowed whole. However, sorafenib tablets can be dispersed in water to facilitate the administration to subjects that cannot swallow tablets.

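### The treatment sections give sorafenib for any FLT3-ITD, although Sections 2.4 and 4.0 set an allelic ratio above 0.1

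*Combined protocol and SAP*

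**What the plan says.** Two places give a ratio. Section 2.4, speaking of this study, names sorafenib as the FLT3 inhibitor "in patients with FLT3-ITD HAR (>0.1) AML". Section 4.0 lists "FLT3 High Allelic Ratio mutations (AR >0.1" among the high-risk markers.

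The treatment sections do not repeat it:

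- **Section 5.2**, Induction I with sorafenib from Day 11: "The following therapy guidelines are for patients during Induction I with FLT3-ITD mutation".
- **Section 5.4**, Induction II with sorafenib: "The following therapy guidelines are for patients during Induction II with FLT3-ITD AML". On transplant it adds: "Patients with FLT3-ITD AML may proceed to best allogenic donor SCT or alternative donor SCT following Induction II".
- **Section 5.6**, Intensification I with sorafenib: "for patients with FLT3-ITD AML who do not have an appropriate donor for SCT".
- **Section 5.8**, Intensification II with sorafenib: "The following Intensification II therapy guidelines are for patients with FLT3-ITD AML who do not have an appropriate donor for SCT".

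None of the four refers back to 2.4 or 4.0. Section 8.1 schedules FLT3 testing on the baseline marrow but mentions neither a ratio nor a turnaround time. Off-study criterion 7 in Section 10.3 refers to FLT3/ITD status, again without a ratio. Section 7.2 requires antibacterial prophylaxis for everyone except children receiving sorafenib.

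**The concern.** For a child whose FLT3-ITD has an AR of 0.1 or less, the plan holds two rules. Section 2.4 excludes that child from sorafenib; Section 5.2, followed as written, prescribes it. No section says which prevails.

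Three things are at stake for such a child. The first is exposure to a drug that the plan meant for others. The second is cardiac: Section 9.6 lists heart failure and left ventricular systolic dysfunction as rare but serious sorafenib toxicities, and 6.3 holds the drug when cardiac function falls, in a trial that aims to spare the heart and has cardiotoxicity as a secondary endpoint. The third is that the requirement for antibacterial prophylaxis no longer applies. This is a question of consistent treatment and patient safety, not of statistical power.

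**Working it through.** The plan states no figure on this point to reproduce. The check compares the text, counts scheduled days, and gives a rough scale.

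**1. Does risk group settle the matter before sorafenib starts?** No. Under 5.2 sorafenib starts on Day 11 of Induction I. Under 4.0 risk group is assigned only once Induction I is over. On Day 11 the working instruction is therefore 5.2, which has no ratio.

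**2. Can FLT3-ITD safely be read as shorthand for AR above 0.1?** Not with confidence. Section 4.0 uses FLT3 in both ways: the high-risk entry gives the ratio, while the low-risk NPM1 entry excludes an associated FLT3 mutation with no ratio. An unqualified FLT3 term in this protocol does not automatically carry the cut-off.

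**3. Which route fits a low-ratio child?** Take AR of 0.1 or less, MRD negative, with no other high-risk marker. Section 4.0 makes this child low risk, so 5.5 and 5.7 (chemotherapy without sorafenib) apply. The label FLT3-ITD AML also fits, so the wording of 5.4 applies too.

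**4. Scheduled sorafenib days for a child with AR of 0.1 or less.**

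| Course | Days | Count |
|---|---|---|
| Induction I (5.2) | 11 to 28 | 28 − 11 + 1 = 18 |
| Induction II (5.4) | 7 to 34 | 34 − 7 + 1 = 28 |
| Intensification I (5.6) | 6 to 33 | 33 − 6 + 1 = 28 |
| Intensification II (5.8) | 11 to 28 | 28 − 11 + 1 = 18 |

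Through Induction II: 18 + 28 = 46 days, against 0 under 2.4. The total reaches 46 + 28 + 18 = 92 days only for a child treated under the FLT3-ITD sections who has no donor and completes all four courses.

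**5. How many children?** Section 2.4 puts activating FLT3 mutations at about 15%, and Section 11.1 expects about 30 patients: 0.15 × 30 = 4.5. This is an upper figure for ITD, because the 15% covers all activating FLT3 mutations. The share with AR of 0.1 or less is not in the documents. Assuming a share q of 5% to 40%, with p = 0.15q and a binomial count in n = 30:

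| Assumed q | p | Expected, 30p | At least one, 1 − (1 − p)^30 | At most two |
|---|---|---|---|---|
| 5% | 0.0075 | 0.225 | 0.202 | 0.9985 |
| 40% | 0.06 | 1.8 | 0.844 | 0.732 |

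The range shows only that the number is small; it is too wide to support anything finer.

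**The case against.** The strongest reply is that the rule is already stated. Section 2.4 gives a direction for this study, 4.0 repeats the cut-off, and nothing in Section 5 says that any ratio qualifies. Read as a whole, the Section 5 headings may simply be shorthand. AR above 0.1 is indeed the likely intent: the transplant sentence in 5.4 copies the one in 5.3, "Patients with high risk status may proceed to best allogenic donor SCT or alternative donor SCT following Induction II", with the patient label changed. But likely intent is not an instruction, and steps 1 and 2 of the working show why the shorthand reading is not secure.

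On transplant the reply largely succeeds. A reader might infer from 5.4, and from the donor wording in 5.6 and 5.8, that the plan sends low-risk children with a low ratio to transplant. The documents do not support that. The 5.4 sentence permits and does not direct. Section 5.4 itself expects a low or high risk classification by the start of Induction II and ties the unrelated-donor search to high risk. The primary objective (1.1), Section 2.1.1, and Sections 5.5 and 5.7 give low-risk children chemotherapy alone. What remains is a wording mismatch.

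Three further points stand in part. The design schema is missing from the text available for review and may show how FLT3 patients are allocated. Section 7.2 removes a requirement and does not forbid prophylaxis. And it would be too quick to infer that adding the ratio to Section 5 is enough: 8.1 does not say that the test reports a ratio by Day 11, and criterion 7 in 10.3 allows for status still unknown when Induction I ends.

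**Conclusion.** The concern holds for sorafenib. Sections 2.4 and 5.2 give conflicting instructions for a child with FLT3-ITD at AR of 0.1 or less, and 5.4, 5.6 and 5.8 continue the mismatch. For each such child the difference is 46 scheduled days of sorafenib through Induction II against none, together with loss of the 7.2 prophylaxis requirement. The transplant sentence should be corrected at the same time but is not itself a conflict of treatment routes.

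The number affected is probably no more than one or two of about 30, on an assumed low-ratio share that the documents do not supply. No sample size or power figure changes, since the trial is sized on feasibility for estimation, and no effect on the event-free survival estimate has been shown. The conclusion rests on the text of the sections named, without sight of the schema. It should be fixed, because the difference for an individual child is material and the remedy is simple.

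**What to change.** 1. Define FLT3-ITD patients once, as FLT3-ITD with AR above 0.1. Alternatively, insert the ratio in the headings and opening lines of 5.2, 5.4, 5.6 and 5.8, and in the 5.4 transplant sentence.
2. State that FLT3-ITD with AR of 0.1 or less follows 5.1 and 5.3 without sorafenib, with the antibacterial prophylaxis of 7.2, and then the Section 4.0 risk group. When doing so, confirm whether the FLT3 exclusion in the low-risk NPM1 entry of 4.0 is meant at any ratio.
3. Specify in 8.1 that the baseline FLT3 test reports the allelic ratio before Day 11 of Induction I.

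If the sponsor in fact wants sorafenib for any FLT3-ITD, Section 2.4 is the text to change; one rule is needed either way.

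The cost is a short amendment, plus confirmation that the laboratory can return a ratio in time. FLT3 testing is already scheduled at baseline, and 4.0 already needs the ratio. The small downside is that sorafenib must wait for that result.
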